8.2.1 Treatment-Emergent Adverse Events by System Organ Class and Preferred Term

The total number of TEAEs and the number and percentage of subjects with events will be presented by system organ class (SOC) and preferred term (PT). Subjects are counted once in each SOC and PT. Percentages will be based on the total number of treated subjects in the treatment group. SOC will be listed in the Internationally Agreed Order (found in MedDRA Data Retrieval and Presentation: Points to Consider, Release 3.2) and PTs within a SOC will be listed alphabetically.

This will be repeated for treatment-related AEs.

8.2.2 Treatment-Emergent Adverse Events by System Organ Class, Preferred Term, and Relationship/Severity

The total number of TEAEs and the number and percentage of subjects with events will be presented by SOC and PT as described above by relationship to study drug (related, not related). At each level (SOC, PT, overall), subjects will be counted as related if they have any TEAE within that level that was deemed related.

Likewise, this presentation will be repeated by severity. Subjects will be counted at the highest severity that they experience with a given level of summarization (SOC, PT, overall).

Additionally, TEAEs related to the study procedure will be displayed as above as well as broken down by severity.

8.2.3 Serious AEs, AEs leading to death, Special Interest and Significant Treatment-Emergent Adverse Events by System Organ Class and Preferred Term

The total number of TEAEs and the number and percentage of subjects with events will be presented by SOC and PT as described above for serious AEs, TEAEs leading to death, special interest TEAEs, and significant TEAEs.

TEAEs of special interest will include TEAEs associated with hypersensitivity, imaging findings, leg pain, and back pain; significant TEAEs will include TEAEs that result in study discontinuation. Specific PTs related to each of the special interest groupings will be described in the define file for the datasets.

The number of TEAEs of special interest and percentage of subjects with events will be summarized by severity and time of occurrence. Time of first occurrence will be based on time from injection and will include the following categories: ≤ 1 day; 2 – 7 days; 8 days to 13 weeks; > 13 weeks.

All the above will be repeated for treatment-related AEs only.

8.3 Vital Signs, Labs, Imaging Findings, and Other Observations Related to Safety

8.3.1 Vital Signs

Vital signs at each visit and changes from baseline will be summarized descriptively using the conventions for continuous variables. A listing of vital signs will be presented by treatment group, subject, vital sign, and visit.

8.3.2 Laboratory Tests

Clinical laboratory tests are collected at screening, Weeks 1, 6, 13 and at discontinuation. Changes from screening will be summarized descriptively using the conventions for continuous variables.

A listing of laboratory results will be presented by treatment group, subject, lab test, and visit. The results of pregnancy tests and urine drug screens will be presented in separate listings.

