 - a. Aspartate aminotransferase (AST) or alanine aminotransferase (ALT) $\geq 2.5 \times$ upper limit of normal (ULN)

- b. Total bilirubin $\geq 1.5 \times$ ULN, unless isolated Gilbert's syndrome
- c. Serum creatinine $\geq 1.5 \times$ ULN
- d. Hepatitis C virus antibody or hepatitis B surface antigen positive. Subjects who have been successfully treated for hepatitis C and currently have undetectable HCV RNA are eligible for study participation.

27. Subjects with a body mass index (BMI) ≥ 40 .

28. Subjects who have difficulties securing an investigational product injection route by the investigator for anatomical reasons.

29. Subjects who are currently hospitalized or have a planned hospitalization during the life of the study.

30. Subjects who have a planned move that may result in difficulty visiting a clinical site(s) during the life of the study.

31. Subjects who previously participated in a clinical study of SI-6603.

32. Subjects who are receiving compensation according to the Workers' Compensation Act or are involved in personal injury litigation due to a lumbar-related injury.

33. Subjects who participated in another interventional clinical study within 30 days prior to the time of informed consent, or who are expected to participate in another study during the period of this study.

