9.6.2 Laboratory Tests

- Assessment Points for All Subjects: Screening visit, Weeks 0, 1, 6, and 13, and discontinuation visit prior to or within Week 13
- Additional Assessment Points for Subjects Receiving Hydrocodone/Acetaminophen Rescue: Week 1, 2, 4, 6, 13, 26 and 39
- Items:
 - Screening visit – urine drug test, serum pregnancy test, blood alcohol test, and hematology, serology markers, hepatic, and chemistry panels.
 - Week 0 – urine drug test, urine pregnancy test.
 - Week 1, Week 6, Week 13 and discontinuation visit (prior to or within Week 13) – hematology and chemistry panels
 - Week 1, 2, 4, 6, 13, 26 and 39 – urine drug test (only for subjects receiving hydrocodone/acetaminophen rescue)
- Method: Urine assessments will be performed at the study sites with provided kits. Blood assessments will be performed by a central laboratory. The investigator or site staff will collect blood samples according to a separately distributed manual. Laboratory variables from blood tests will be determined as listed in Table 2.

Table 2 Laboratory Assessments

Hematology:	hematocrit hemoglobin platelets red blood cell count white blood cell count with differential
Clinical chemistry:	creatinine C-reactive protein total protein total bilirubin direct bilirubin (determined if total bilirubin is elevated) total cholesterol urea nitrogen uric acid
Electrolytes:	calcium chloride magnesium potassium sodium
Liver enzymes:	alkaline phosphatase AST ALT lactic dehydrogenase γ-glutamyl transpeptidase albumin
Serological markers (at screening only)	Hepatitis B surface antigen Hepatitis C antibody; hepatitis C RNA only when required for documentation of sustained virologic response to reported effective treatment. HIV

AST = aspartate aminotransferase; ALT = alanine aminotransferase; HIV = human immunodeficiency virus

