10.1.3 Vital Signs and Laboratory Tests

If an abnormal laboratory finding or vital sign is observed, the investigator should judge whether it is an AE or not by referring to the following criteria:

- When any medical intervention such as pharmacotherapy or surgical care is performed in order to improve the abnormality, or
- Other than case above, when investigator judges that the abnormality is medically important and should be considered an AE.

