11.8.2 Visit Window and Unscheduled Assessments

All data collected during follow-up will be displayed and analyzed according to the actual visit date in the eCRF. Assessments taken outside of protocol-allowable windows will be displayed according to the eCRF assessment recorded by the investigator. Unscheduled assessments (laboratory data or vital signs associated with non-protocol clinical visits or obtained in investigating or managing AEs) will be included in listings but not summaries of the data.

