3. GENERAL ANALYSIS AND REPORTING CONVENTIONS

All efficacy analyses will use a two-sided alpha = 0.05 test unless otherwise stated. P-values will be rounded to four decimal places. If a p-value is less than 0.0001, it will be reported as “<0.0001.”

Continuous data will be described using descriptive statistics: sample size, mean, SD, median, Q1 and Q3, minimum, and maximum. Minimums and maximums will be reported with the same precision as the raw values; medians, Q1, Q3 and means will show precision to one decimal place greater than the raw values; SDs will show precision to two decimal places greater than the raw values. For example, if height is recorded in whole centimeters, min and max will be displayed as whole centimeters, means will be shown as xxx.x and SD will be shown as xxx.xx. Data will be displayed in all listings sorted by treatment group and subject identification number. Subjects will be identified in the listings by the subject identification number concatenated with the investigator number.

When count data are presented, the percentage will be suppressed when the count is zero in order to draw attention to the non-zero counts. The denominator for all percentages will be the number of subjects with non-missing data in that treatment group within the population of interest.

For the duration of leg pain covariate, if partial dates are provided, then missing dates will be imputed as the 15th for a missing day and July for a missing month, consistent with prior protocols.

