7.1.2 Assessment Time Windows

All data collected during follow-up will be displayed and analyzed according to the actual visit that the data are assigned in the eCRF.

Study discontinuation visits will be assigned to the corresponding visit if it falls within the protocol window for that visit. For example, a discontinuation visit on day 100 would be assigned to Week 13 since it falls within the -7/+14 day window for Week 13.

However, if scheduled visit data are present, then the discontinuation visit data will not be used for that visit. This will be done on a parameter level and discontinuation visit values will not be assigned to visits where the assessment was not scheduled to be taken (For example, Week 4 does not have MRI, but the discontinuation visit does; even if the discontinuation visit falls in the Week 4 window, we would not assign the MRI findings to a Week 4 visit).

Unscheduled assessments (laboratory data, imaging findings or vital signs associated with non-protocol clinical visits or obtained in investigating or managing AEs) will be included in listings but not summaries of the data. Likewise, discontinuation visit data that do not fall within a protocol-defined window or fall within a window where

scheduled visit data are already present will not be summarized, but will appear in listings.

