8.3.3 Imaging Findings

Counts and percentages of significant findings from the MRI and X-ray imaging will be presented by treatment for screening, Week 13 and Week 52; results from discontinuation visit and last visit for all subjects will be presented separately.

Findings to be presented will include:

- Disc height (disc index): decrease in disc height $\geq 30\%$ compared to baseline value
- Vertebral posterior angle: vertebral body angle formed by flexion of $\geq 5^\circ$
- Vertebral body translation: vertebral body translation of ≥ 3 mm
- Changes of vertebral body endplates and adjacent bone marrow as visible by MRI. The criteria are as follows: Modic Type 1, Type 2, or Type 3 change in vertebral body endplates and adjacent bone marrow.

Disc height, vertebral posterior angle, and vertebral body translation will be summarized by visit for the observed values, the change from baseline, and the percent change from baseline (disc height only). Percent change from baseline in disc height, observed value of vertebral posterior angle and vertebral body translation will also be summarized in a line graph over time.

Summaries will use the adjudicated values, but all reader data will appear in the listings.

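### SAP 8.3.2 plans laboratory data only as continuous change from screening plus listings, so subjects who leave the reference range are not counted by arm unless recorded as AEs

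*SAP*

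**What the plan says.** SAP 8.3.2 lists the collection points (screening, Weeks 1, 6 and 13, and discontinuation) and plans one summary: "Changes from screening will be summarized descriptively using the conventions for continuous variables". It adds a listing by group, subject, test and visit. The conventions it refers to are in SAP 3: "Continuous data will be described using descriptive statistics: sample size, mean, SD, median, Q1 and Q3, minimum, and maximum". Neither document describes a shift table, an out-of-range count or a post-injection threshold for laboratory values. SAP 11 records no change to the laboratory analyses, and Protocol 11.7 asks only for a summary by treatment group.

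Protocol 10.1.3 gives two routes by which an abnormal value becomes an AE: it was medically treated, or "when investigator judges that the abnormality is medically important and should be considered an AE". Leaving the reference range is not itself a criterion.

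Unscheduled samples stay out of the tables. SAP 7.1.2 says those "obtained in investigating or managing AEs) will be included in listings but not summaries of the data", and Protocol 11.8.2 agrees.

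The haematology panel in Protocol 9.6.2, Table 2 includes "white blood cell count with differential", and the clinical chemistry group includes C-reactive protein and creatinine.

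**The concern.** A reader of the planned tables could see how the average laboratory value moved in each arm, but not how many subjects became abnormal. The planned maximum is a maximum change. A large rise may start from a low value and stay within range, and a small one may cross the limit, so it cannot be read against an upper limit of normal (ULN).

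The secondary safety objective asks whether the 1.25 U dose is safe and tolerated. Protocol 1.2.1.1 describes the product as a foreign protein and lists raised eosinophil counts among events seen in earlier studies. Protocol 1.2.1.5 names infection at the injection site. The differential and CRP are the blood tests closest to those two risks. A rise that was neither treated nor judged important would appear only in the spread or extreme of the changes, or in a listing. A count could be built from the listing later, but any threshold above the reference limit would then be chosen with the data in view.

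**Working it through.** The plan states no laboratory figure to reproduce. The check compares the planned summaries, then asks what a mean-change table and a count table could each show at this sample size.

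**1. Planned summaries side by side**

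| Domain | Observed values | Change | Counts by arm |
|---|---|---|---|
| Vital signs (SAP 8.3.1) | yes | yes | none described |
| Imaging (SAP 8.3.3) | yes | yes | yes, against fixed thresholds |
| AEs (SAP 8.2) | – | – | yes, with exact 95% CI in the overall display |
| Laboratory (SAP 8.3.2) | not described | yes | none described |

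**2. How many tests are involved**

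Table 2 groups are haematology 5 (differential counted with white cells), clinical chemistry 8, electrolytes 5 and liver 6. Post-injection visits with blood tests are Weeks 1, 6 and 13. Protocol 9.6.2 names a hepatic panel only at screening and then haematology and chemistry panels, so the total depends on how the panels are read:

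- Haematology and clinical chemistry only: (5 + 8) × 3 = 39 test-by-visit summaries.
- With electrolytes: 18 × 3 = 54.
- With liver tests: 24 × 3 = 72.

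On any reading, the text gives a count of abnormal subjects for none of them. White cells, the differential, CRP and creatinine fall within the narrowest reading.

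**3. Sample size used**

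The plan gives 160 per arm. Its inputs (12 mm, SD 30 mm, 90% power, two-sided 5%) give 2 × (1.960 + 1.282)² × (30/12)² ≈ 132 per arm. Then 132/0.85 ≈ 156, consistent with 160. After 15% dropout, 160 × 0.85 = 136.

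**4. Sensitivity of the mean change** (rates and rises assumed, not in the documents)

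If a share p of one arm rises by k SD, that arm's mean moves by p × k SD. The standard error of the arm difference is √(2/160) = 0.112 SD.

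- p = 2% (about 3 subjects): k = 2 gives 0.04 SD; k = 4 gives 0.08 SD.
- p = 5% (8 subjects): k = 2 gives 0.10 SD; k = 4 gives 0.20 SD.

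Even the largest, 0.20/0.112 = 1.8 standard errors, is below 1.96. A count shows the same 8 subjects directly: 8/160 = 5.0%, exact 95% CI 2.2–9.6%.

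**5. Precision of the counts**

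With no events, the exact 95% upper limit is 1 − 0.025^(1/n): 2.3% at n = 160 and 2.7% at n = 136.

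The half-width for an arm difference is 1.96 × √(2p(1 − p)/n), with background p assumed equal in both arms:

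| p (assumed) | n = 160 | n = 136 |
|---|---|---|
| 2.5% | 3.4 points | 3.7 points |
| 5% | 4.8 points | 5.2 points |

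Only differences larger than these would stand out.

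**The case against.** The strongest reply is that AE reporting already covers the named risks. The eosinophil rise in Protocol 1.2.1.1 was itself reported as an AE in earlier studies. Hypersensitivity is an event of special interest, counted by arm with an exact interval. Any infection recorded as a treatment-emergent event is tabulated by organ class and term, and Protocol 1.2.1.5 says such events may follow the sham procedure too. This reply stands for values that become AEs. It does not reach values left unrecorded because nobody treated them or thought them important.

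Second, central-laboratory reference ranges are not the analyst's choice, so a low/normal/high table made later would not be data-driven. That is fair. The case for fixing limits in advance applies mainly to any higher multiple.

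Third, counts across many tests, with half-widths of several points, will include chance exceedances. That is also true, and it is a reason to keep the threshold list short.

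Fourth, the protocol's risk section names no hepatic or renal risk, so limits for AST, ALT, bilirubin and creatinine would be borrowed from exclusion criterion 26 and not based on risk. They are a convenience and not the core of the point.

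Fifth, table shells may exist. SAP 14 is an attachments heading with no content in the supplied text, so the finding is limited to what can be read.

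A reader might also infer that the handling of discontinuation samples is left open, because imaging has its own sentence ("results from discontinuation visit and last visit for all subjects will be presented separately") and laboratory tests have none. The documents do not support that. SAP 7.1.2 assigns a discontinuation visit to a scheduled visit when it falls in that window, the test was due then and no scheduled value exists; otherwise the data are listed only. The section sits in the efficacy chapter, but it covers all follow-up data and names laboratory data.

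**Conclusion.** The point holds as a minor improvement to safety presentation. The visible SAP text gives changes and listings but no per-arm count of subjects whose laboratory values became abnormal, and AE recording fills only part of that gap.

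Stronger readings do not hold. The SAP does not depart from the protocol, because Protocol 11.7 is met. The data are not lost, because individual values are listed and extreme changes are shown. The objective is to find out whether the drug is safe, so the plan does not claim safety in advance. No primary or key secondary result, alpha or power is affected.

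The insensitivity of the mean (0.04–0.20 SD against a standard error of 0.11 SD) rests on assumed rates of 2–5% and rises of 2–4 SD. The precision of counts (half-width 3.4–5.2 points) rests on an assumed 2.5–5% background in both arms. That the text plans no such count rests on neither assumption.

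**What to change.** Before unblinding, add to SAP 8.3.2, by arm:

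- Low/normal/high shift tables from screening to Weeks 1, 6 and 13.
- The number and percentage of subjects, with exact 95% CI as in SAP 8.2, above limits fixed in advance for eosinophils, white cells and CRP: the central-laboratory ULN and one stated higher multiple.
- If wanted, the entry limits for creatinine (1.5 × ULN) and, where drawn after injection, AST/ALT (2.5 × ULN) and bilirubin (1.5 × ULN). Table 2 lists total bilirubin under clinical chemistry, so the doubt is mainly about AST and ALT. Subjects at or above these limits are excluded at entry (apart from isolated Gilbert's syndrome for bilirubin), so later exceedances would be essentially new.
- Optionally, one descriptive row for the worst post-injection value that includes unscheduled samples and out-of-window discontinuation samples (for example Days 10–35 or 51–84, which fall in no laboratory visit window). Label it as dependent on how often each subject was sampled, and record it in SAP 11.

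If shells in SAP 14 already contain shift tables, a sentence in 8.3.2 pointing to them covers the first item.

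The cost is a few tables from central-laboratory data already collected. The downsides are chance exceedances in both arms, imprecise small counts, and the dependence of the optional row on sampling frequency.

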8.3.3 Imaging Findings

Counts and percentages of significant findings from the MRI and X-ray imaging will be presented by treatment for screening, Week 13 and Week 52; results from discontinuation visit and last visit for all subjects will be presented separately.

Findings to be presented will include:

- Disc height (disc index): decrease in disc height $\geq 30\%$ compared to baseline value
- Vertebral posterior angle: vertebral body angle formed by flexion of $\geq 5^\circ$
- Vertebral body translation: vertebral body translation of ≥ 3 mm
- Changes of vertebral body endplates and adjacent bone marrow as visible by MRI. The criteria are as follows: Modic Type 1, Type 2, or Type 3 change in vertebral body endplates and adjacent bone marrow.

Disc height, vertebral posterior angle, and vertebral body translation will be summarized by visit for the observed values, the change from baseline, and the percent change from baseline (disc height only). Percent change from baseline in disc height, observed value of vertebral posterior angle and vertebral body translation will also be summarized in a line graph over time.

Summaries will use the adjudicated values, but all reader data will appear in the listings.

8.3.4 Post Treatment Lumbar Surgery

Counts and percentages of subjects with post-treatment lumbar surgery by Week 52 will be presented by treatment. Percentages will be out of subjects with successful contact.

This will be summarized for any surgery, LDH at a non-target level and surgery not for LDH.

9. OTHER ANALYSES

The association between imaging findings and clinical symptoms will be assessed. The following dichotomous imaging findings will be evaluated:

- Disc height (disc index): decrease in disc height $\geq 30\%$ compared to baseline value
- Vertebral posterior angle: vertebral body angle formed by flexion of $\geq 5^\circ$
- Vertebral body translation: vertebral body translation of ≥ 3 mm
- Changes of vertebral body endplates and adjacent bone marrow as visible by MRI: Change of Modic Type 1, Type 2 and Type 3

For each outcome, treatment and level (decrease in disc height $\geq 30\%$ and decrease in disc height $< 30\%$, for example) the following will be reported:

- Subjects with TEAEs associated with leg pain (number and percentage)
- Subjects with TEAEs associated with back pain (number and percentage)
- Subjects with worsening of worst leg pain (number and percentage)
- Subjects with worsening of worst back pain (number and percentage)
- Continuous summary statistics of worst leg pain
- Continuous summary statistics of worst back pain

These will be reported through Week 13 and Week 52.

10. INTERIM ANALYSES

No interim analyses are planned. All final analyses will be performed following database lock and unblinding.

11. CHANGES TO THE ANALYSES PLANNED IN THE PROTOCOL

The protocol-specified MI sensitivity analysis to the primary did not include consideration for subject data that is set to missing following a prohibited procedure; this has been included among the study outcomes that use the baseline distribution for imputation.

The multiple comparison algorithm has been updated to do a more straightforward serial gatekeeping approach.

The recurrence of LDH endpoint in the protocol references one of the treatment failure criteria; because this criteria was nested in other requirements that would conflict with the recurrence of LDH criteria, the text was updated to focus on only the applicable items. Additionally, surgical intervention was removed as a criteria and the symptom criteria were clarified.

